8.1. None

- 9. Subject Costs:
  - 9.1. All tests and procedures involved in this study are considered standard of care and would be the responsibility of the patient and/or insurance. Vitamin E is available over the counter and trental is available by prescription.

#### Appendix A

Two-Stage Clinical Trials Sample Size (Results are in the form of NON-RN as success)

## **TO DETECT RN REDUCTION FROM 15% (HISTORICAL) to 10%** (a 33.3% reduction)

#### Possible Designs For P0=0.850, P1=0.900, Alpha=0.050, Beta=0.200

								Constraints
N1	R1	PET	Ν	R	Ave N	Alpha	Beta	Satisfied
124	106	0.598	288	254	189.88	0.047	0.198	Optimum

In the first stage, we need to see 124 lesions on supplement and if we find 106 or less lesions RN-free, the trial stops. If you find 107 or more lesions RN free, the trial continues and we go all the way to 288 lesions. If we find 255 or more lesions RN free (in other words- 33 or fewer RN), we have proven that the trial succeeded in reducing the RN incidence from 15% to 10% by giving them supplement.

# **TO DETECT RN REDUCTION FROM 15% (HISTORICAL) to 7.5%** (a 50 % reduction)

#### Possible Designs For P0=0.850, P1=0.925, Alpha=0.050, Beta=0.200

N1	R1	РЕТ	Ν	R	Ave N	Alpha	Beta	Constraints Satisfied
52	44	0.528	134	120	90.69	0.047	0.2000pti	mum & Minimax

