      - 4.4.1.2. Secondary
        - 4.4.1.2.1. Change in volume of contrast enhancement
        - 4.4.1.2.2. Change in volume of necrosis

- 4.4.1.2.3. Change in volume of T2 edema
- 4.4.1.2.4. Steroid usage
- 4.4.2. Results of the Data analyses will be reported over all as well as by stratifying with respect to:
  - 4.4.2.1. Radiation prescription dose
  - 4.4.2.2. Lesion volume
  - 4.4.2.3. Presence of comorbidities: Hypertension, Diabetes
- 4.4.3. As per the design, at the first stage we would evaluate the results by identifying when we have 8 lesions with necrosis. If at that stage, we have 52 or more lesions in the study then that would confirm we should continue to complete the study with all 134 lesions. At that stage, if we find 14 or less lesions with radiation necrosis, we would then claim that the study has met its objective of a 50% reduction in incidence of radiation necrosis (from 15% to 7.5%). (see Appendix A)
- 4.4.4. Summary of Data Submission (See Appendix B)

Follow MRI Form (MF)

- 4.4.4.1. Enrollment Form (EF)
- 4.4.4.2. Initial Evaluation Form (IF)
- 4.4.4.3. Treatment Form (TF)
- 4.4.4.4. Follow Up Form (FF)
- Within 2 wks of registration Within 2 wks of registration At the end of radiosurgery
- Every 3 months for 1 year
- Every 3 months for 1 year
- 4.4.5. Treatment Form (TF) will be completed by treating physician.
- 4.4.6. MRI documentation

4.4.4.5.

- 4.4.6.1. The contrast-enhanced MRI performed pre-radiosurgery and every 3 months post-radiosurgery will be evaluated by the investigators: REW, JB, LI. Form MF will be completed by investigator LI.
- 4.4.6.2. Radiation necrosis will be defined as previously reported by Blonigen et al. (4):

A combination of criteria will be used including appearance on serial MRI scans, MR Spectroscopy and histology (when available). It will be further described as the following: (1) patient with radiographic changes with a requirement of steroid therapy, (2) 2 consecutive scans with persistent MRI changes consistent with radiation necrosis, (3) findings suggestive of radiation necrosis on MR Spectroscopy, or (4) histological evidence of radiation necrosis.

- 4.4.6.3. Once radiation necrosis is identified by the treating physician, parameters will be quantified using standard radiation oncology software tools by an investigator: LI. The volume of contrast enhancement, T2 edema and necrosis will be quantified.
- 4.5. Data storage and confidentiality

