  - 4.5.1. Data will be maintained in a password protected database and will only be accessed by the listed investigators. The information gathered will not be used or disclosed for any other purpose other than this specific research project.

- 5. Estimated period of time to complete the study.
  - 5.1. It is estimated that the patient recruitment period will be 2 years and the follow up period will be one year. Total estimated time to complete the study is 3 years.
- 6. Human Subjects: Describe the characteristics of the research population:
  - 6.1. Subjects will include patients receiving or planning to undergo single fraction or five fraction radiosurgery for a metastatic brain tumor.
  - 6.2. The demographics of the study population are expected to reflect the general population with intracranial metastatic tumors. Only adults  $\geq$  18 years of age will be included in the study.
  - 6.3. Recruitment:
    - 6.3.1. Patients seen at the University of Cincinnati Brain Tumor Center will be directly recruited by the treating physician.
  - 6.4. This study is estimated to require 49 patients. In a recently published study performed at the University of Cincinnati (4), patients recruited to the study had an average of 2.75 metastatic lesions. Each lesion was treated independently when analyzing the incidence of radiation necrosis. Using this same method, a total of 134 lesions are necessary to show a 50% effective reduction in radiation necrosis with our supplement. This would be estimated to require 49 patients.
  - 6.5. Inclusion Criteria:
    - 6.5.1. Patients about to undergo or currently receiving single or five fraction radiosurgery for a metastatic brain tumor.
    - 6.5.2. Diagnosis of a metastatic brain tumor may be accomplished by histologic confirmation or by clinical confirmation by the treating physician based on MR Imaging characteristics in the setting of a known history of cancer.
    - 6.5.3. Availability for follow up
    - 6.5.4. Ability to give informed consent.
    - 6.5.5. Age  $\geq$  18 years
    - 6.5.6. Patients who have had partial or total resection of a metastatic tumor are eligible.
  - 6.6. Exclusion Criteria:
    - 6.6.1. Known sensitivity to vitamin E or Trental
    - 6.6.2. Pregnant or nursing women.
    - 6.6.3. Recent intracranial bleed or retinal hemorrhage

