#### **Report Definitions**

N1 is the sample size in the first stage.
R1 is the drug rejection number in the first stage.
PET is the probability of early termination of the study.
N is the combined sample size of both stages.
R is the combined drug rejection number after both stages.
Ave N is the average sample size if this design is repeated many times.
Alpha is the probability of rejecting that P<=P0 when this is true.

Beta is the probability of rejecting that P>=P1 when this is true.
P0 is the response proportion of a poor drug.
P1 is the response proportion of a good drug.

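### The adopted two-stage design (52/44, 134/120) has beta 0.144 rather than the printed 0.200, and is neither optimum nor minimax

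*Combined protocol and SAP*

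**What the plan says.** Appendix A treats freedom from radiation necrosis (RN) as success and offers three Simon two-stage designs. The trial adopts the one for RN falling from 15% to 7.5%, headed "Possible Designs For P0=0.850, P1=0.925, Alpha=0.050, Beta=0.200". Its row reads "52 44 0.528 134 120 90.69 0.047 0.2000pti mum & Minimax". Text extraction has run the beta of 0.200 into the word Optimum. The columns are N1, R1, PET, N, R, Ave N, alpha, beta and the label.

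The body of the protocol relies on this row in two places:

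- Section 6.4 says that "a total of 134 lesions are necessary to show a 50% effective reduction in radiation necrosis" and converts that to 49 patients.
- Section 4.4.3 uses 52 and 134 lesions and states the final rule: "if we find 14 or less lesions with radiation necrosis, we would then claim that the study has met its objective". The objective it names is a "50% reduction in incidence of radiation necrosis (from 15% to 7.5"%, which matches P1 = 0.925.

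Two places fix the meaning of R. The Report Definitions say "R is the combined drug rejection number after both stages". The worked 288-lesion example, with R = 254, reads "If we find 255 or more lesions RN free (in other words- 33 or fewer RN".

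**The concern.** This row is the plan's whole justification for its power and sample size. If its printed beta does not belong to its own N1, R1, N, R and P1, the stated power is wrong. If the row is not the smallest or most economical design meeting the targets, section 6.4 has no basis for calling 134 lesions necessary.

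The final cutoff is tied to the same row. A total of 134 with R = 120 means the drug is rejected at 120 or fewer RN-free lesions, so success starts at 121 (13 or fewer RN). Section 4.4.3 starts success at 120 RN-free (14 RN). Correcting beta alone would therefore still leave operating characteristics that do not describe the rule the trial will apply.

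**Working it through.** **Inputs.** P0 = 0.850, P1 = 0.925, target alpha 0.050, target beta 0.200, N1 = 52, R1 = 44, N = 134 and R = 120, all from the Appendix A row. Lesions are taken as independent, the method section 6.4 adopts.

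**Formulas.** Let X1 ~ Bin(N1, p) be the RN-free count at stage 1 and X2 ~ Bin(N − N1, p) the count at stage 2.

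- PET(p) = P(X1 ≤ R1)
- Ave N = N1 + [1 − PET(P0)] × (N − N1)
- Pass(p) = Σ over x from R1 + 1 to N1 of P(X1 = x) × P(X2 > R − x)
- alpha = Pass(P0); beta = 1 − Pass(P1)

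**Step 1: the adopted row.**

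| Quantity | Printed | Exact |
|---|---|---|
| PET at 0.85 | 0.528 | 0.5281 |
| Ave N | 90.69 | 52 + 0.4719 × 82 = 90.69 |
| alpha | 0.047 | 0.0471 |
| beta at 0.925 | 0.200 | 1 − 0.8563 = **0.1437** |

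Three of the four figures match, so the reading of N1, R1, N and R is right. Only beta fails.

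**Step 2: the same code on the other two rows.**

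| Design | PET | Ave N | alpha | beta |
|---|---|---|---|---|
| 124/106, 288/254 (P1 = 0.90) | 0.598 | 189.88 | 0.0475 | 0.198 |
| 13/11, 65/59 (P1 = 0.95) | 0.602 | 33.71 | 0.0486 | 0.1995 |

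These agree with the printed figures, beta included. The method is not the cause of the gap.

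**Step 3: is the row optimum or minimax?** All designs with N from 60 to 200 were enumerated at P0 = 0.85, P1 = 0.925, alpha ≤ 0.05 and beta ≤ 0.20.

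| Design | N | Ave N | alpha | beta |
|---|---|---|---|---|
| Smallest Ave N: 47/41, 130/116 | 130 | 69.69 | 0.0499 | 0.194 |
| Smallest N: 109/98, 113/101 | 113 | 109.21 | 0.0489 | 0.198 |
| In between: 53/46, 116/104 | 116 | 71.89 | 0.0498 | 0.198 |
| Best Ave N at N = 134: 45/39, 134/120 | 134 | 72.96 | 0.0406 | 0.196 |
| Adopted: 52/44, 134/120 | 134 | 90.69 | 0.0471 | 0.144 |

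The adopted row is beaten on N by 134 − 113 = 21 lesions and on Ave N by 90.69 − 69.69 = 21.00. Even with N held at 134, another stage-1 rule has a lower Ave N.

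**Step 4: could another alternative explain the row?** At P1 = 0.920 the adopted row has power 0.8003, so beta is 0.1997, which rounds to the printed value. A run at 8% RN is thus possible, but the documents state 7.5% throughout, so this stays a conjecture. It would not rescue the label either: at 0.920 the smallest N is 132 (120/107, 132/118) and the smallest Ave N is 80.97 (44/38, 154/137).

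**Step 5: the cutoff in 4.4.3.** Fourteen or fewer RN means 134 − 14 = 120 or more RN-free, which is R = 119. With R1 = 44:

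| Success rule | R | alpha | power at 7.5% RN |
|---|---|---|---|
| 13 or fewer RN (Appendix A) | 120 | 0.047 | 0.856 |
| 14 or fewer RN (4.4.3) | 119 | 0.077 | 0.903 |

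The printed pair 0.047/0.200 describes neither rule.

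**The case against.** The case against concedes the beta error but argues that little follows from it.

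- **It is conservative.** Alpha is right, true beta is better than target, and no decision changes. This stands for R = 120. It does not cover 4.4.3, whose cutoff takes alpha above 0.05.
- **The label fails elsewhere too.** The 288-lesion row is also marked optimum, yet 127/109, 287/253 meets the targets (alpha 0.0487, beta 0.1999) with smaller N and Ave N 184.52. This is correct. It shows that the label is unreliable in more than one row; it does not make it true of the adopted one.
- **The 113-lesion design is impractical.** Its interim look comes at 109 of 113 lesions. Agreed, but 53/46, 116/104 has a normal interim and also meets both targets.
- **Section 6.4 names no power, and independence is doubtful.** Section 6.4 takes its 134 from a row with a stated target beta of 0.200, so 80% is the implied basis. The clustering point stands. With 2.75 lesions per patient and an assumed intraclass correlation of 0.05 to 0.2 (the documents give none), the design effect 1 + 1.75 × ICC is 1.09 to 1.35, which takes 113 lesions to about 123 to 153. The finding is therefore no reason to cut the lesion count.
- **The 0.077/0.903 pair does not match 4.4.3 literally.** Read to the letter, the interim rule continues with at most 7 RN in the first 51 lesions, giving alpha 0.078 and power 0.905. The difference is immaterial.
- **The cutoff is a separate error.** It has its own cause, but the corrected power cannot be stated without choosing a cutoff, so the two must be edited together.

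**Conclusion.** The concern holds. Under the plan's own assumptions (independent lesions, 15% against 7.5% RN), beta for 52/44, 134/120 is 0.144, a 5.6-point understatement of power. The optimum and minimax label is false on both counts, and 134 lesions is not the minimum for 80% power.

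The beta error does not leave the trial underpowered, and its own consequence is limited to a wrong stated power and sample-size rationale. The anti-conservative part is the linked cutoff: as section 4.4.3 is written, alpha is 0.077 against a target of 0.05. The correction should be made, but it does not call the size of the trial into question.

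**What to change.** Make these text changes together:

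1. **Appendix A, 15% to 7.5% row:** change beta to 0.144 and delete the optimum and minimax label. The optimum label on the 288-lesion row should go as well.
2. **Section 6.4:** replace the claim of necessity with a statement such as: 134 lesions give about 86% power at 7.5% RN, assuming independent lesions, with success requiring at least 121 RN-free lesions (13 or fewer RN).
3. **Section 4.4.3:** reconcile the final cutoff with R = 120. If 14 is kept, report alpha 0.077 and power 0.903 in Appendix A and 6.4 instead, and acknowledge that the 0.05 target is exceeded.

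Re-running the design is optional. A switch to 47/41, 130/116 should disclose that the chance of wrongly stopping at stage 1 when RN is truly 7.5% rises from 3.9% to 13.8%.

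The cost is wording in three places. No lesions, patients or visits are added.

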#### FOR A REDUCTION OF RN FROM 15% to 5% (a 66.7% reduction)

Possible Designs for P0=0.85, P1=0.950, Alpha=0.050, Beta=0.200							) Constraints	
N1	R 1	PET	Ν	R	Ave N	Alpha	Beta	Satisfied
13	11	0.602	65	59	33.71	0.049	0.200	Optimum

#### **Report Definitions**

N1 is the sample size in the first stage.
R1 is the drug rejection number in the first stage.
PET is the probability of early termination of the study.
N is the combined sample size of both stages.
R is the combined drug rejection number after both stages.
Ave N is the average sample size if this design is repeated many times.
Alpha is the probability of rejecting that P<=P0 when this is true.

Beta is the probability of rejecting that P>=P1 when this is true.
P0 is the response proportion of a poor drug.
P1 is the response proportion of a good drug.

#### **Summary Statements**

The optimal two-stage design to test the null hypothesis that  $P \le 0.850$  versus the alternative

that P>=0.950 has an expected sample size of 33.71 and a probability of early termination of

0.602. If the drug is actually not effective, there is a 0.049 probability of concluding that it is (the target for this value was 0.050). If the drug is actually effective, there is a 0.200 probability of concluding that it is not (the target for this value was 0.200). After testing the drug on 13 lesions in the first stage, the trial will be terminated if 11 or fewer respond. If the trial goes on to the second stage, a total of 65 lesions will be studied. If the total number responding is less than or equal to 59, the drug is rejected.

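### Appendix A words only designs that were not adopted, and the rule in section 4.4.3 does not match the adopted 52/134 row: success at 14 or fewer necrotic lesions raises alpha from 0.047 to about 0.08

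*Combined protocol and SAP*

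**What the plan says.** Section 4.4.3 gives the working rule in words. It looks at the data when 8 lesions have RN. If 52 or more lesions are in the study by then, "we should continue to complete the study with all 134 lesions". It then claims a 50% reduction, from 15% to 7.5%, if 14 or fewer lesions have RN, and refers the reader to Appendix A. Section 6.4 repeats the size: "a total of 134 lesions are necessary to show a 50% effective reduction in radiation necrosis with our supplement", estimated at 49 patients.

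Appendix A counts RN-free lesions as successes and lists three designs, each against a null RN-free proportion of 0.85:

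- RN 10%: 124 then 288 lesions, with the rule explained in words.
- RN 7.5%: headed "Possible Designs For P0=0.850, P1=0.925, Alpha=0.050, Beta=0.200", a table row only, with N1 = 52, R1 = 44, N = 134, R = 120, PET 0.528, average N 90.69, alpha 0.047 and beta 0.200.
- RN 5%: 13 then 65 lesions, with a table row and the Summary Statements.

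The Summary Statements say "After testing the drug on 13 lesions in the first stage, the trial will be terminated if 11 or fewer respond", then "If the trial goes on to the second stage, a total of 65 lesions will be studied" and "If the total number responding is less than or equal to 59, the drug is rejected". They do not say that this design was set aside. The Report Definitions describe R1 and R as drug rejection numbers.

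**The concern.** A reader who follows the cross-reference from 4.4.3 should find the governing rule. Instead, prose rules are given for the two designs not in use, and the one in use has only a row of figures. Nothing in the appendix marks that row as chosen.

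The gap matters because Appendix A is where the counts in 4.4.3 would be checked. The row is stated in RN-free lesions and 4.4.3 in RN lesions, and the conversion appears to have gone wrong by one lesion at each boundary. If 4.4.3 is applied as written, the trial can claim its objective on a result that the adopted design classes as failure, with a false-positive rate above the 0.05 target.

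**Working it through.** **Inputs.** Null RN-free proportion 0.85 and alternative 0.925; row 52/44, 134/120 (Appendix A, 15% to 7.5% table). R1 and R are rejection numbers (Report Definitions). Limits of 8 RN at 52 lesions and 14 RN at 134 lesions (4.4.3). Mean of 2.75 lesions per patient (6.4).

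**Formulas.** X1 is the RN-free count in the first n1 lesions and X2 the count in the remaining N − n1, both binomial with probability p.

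- PET = P(X1 ≤ R1)
- Average N = n1 + (1 − PET)(N − n1)
- P(success) = sum over x from R1 + 1 to n1 of P(X1 = x) · P(X2 ≥ R + 1 − x). This is alpha at p = 0.85 and power at p = 0.925.

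**Step 1: reproduce the printed rows.**

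| Design | PET | Average N | Alpha | Exact beta | Printed beta |
|---|---|---|---|---|---|
| 124/106, 288/254 (RN 10%) | 0.598 | 189.88 | 0.0475 | 0.198 | 0.198 |
| 52/44, 134/120 (RN 7.5%) | 0.528 | 90.69 | 0.0471 | 0.144 | 0.200 |
| 13/11, 65/59 (RN 5%) | 0.602 | 33.71 | 0.0486 | 0.1995 | 0.200 |

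Everything reproduces except the beta of the adopted row. Average N for that row is 52 + (1 − 0.5281) × 82 = 90.69. Its exact power at 0.925 is 1 − 0.1437 = 0.856. The printed 0.200 is matched at an alternative of 0.92 (0.1997). The Summary Statements are thus an accurate account of the third row.

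**Step 2: identify the adopted design.** The 52 lesions, 134 lesions and 7.5% target in 4.4.3 fit only the second row. 134 / 2.75 = 48.7, hence the 49 patients of 6.4. The 13/65 design would need 65 / 2.75 = 23.6, about 24.

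**Step 3: convert the adopted row to RN counts.** The appendix shows the method for 288 lesions: R = 254 means success at 255 or more RN-free, so 288 − 255 = 33 or fewer RN. In the same way:

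- Final: R = 120 means success at 121 or more RN-free, so 134 − 121 = 13 or fewer RN. Rejection is at 134 − 120 = 14 or more.
- Stage 1: R1 = 44 means stop at 44 or fewer RN-free, so 52 − 44 = 8 or more RN.

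In 4.4.3, 14 RN is success, and an 8th RN with exactly 52 lesions in the study means continue.

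**Step 4: effect on the error rates.**

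| Stage 1 | Final success | Alpha | Power at RN 7.5% |
|---|---|---|---|
| Stop at 8 RN in 52 (row) | 13 or fewer RN (row) | 0.0471 | 0.856 |
| Stop at 8 RN in 52 (row) | 14 or fewer RN (4.4.3) | 0.077 | 0.903 |
| Continue at 8 RN in 52 | 14 or fewer RN (4.4.3) | 0.081 | 0.917 |
| Continue at 8 RN in 52 | 13 or fewer RN (row) | 0.0488 | 0.866 |

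The final count does the damage. The stage-1 difference alone leaves alpha below 0.05. A strictly sequential reading of 4.4.3 continues only if the 8th RN is the 52nd lesion or later, so it stops on 8 or more RN in the first 51. Putting n1 = 51, R1 = 43, N = 134, R = 119 into the same formula gives alpha 0.078, inside the range above.

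**The case against.** The strongest reply is that the body of the protocol settles the choice of design. 4.4.3 names 52, 134 and 7.5% before it cites the appendix, 6.4 repeats 134, and each scenario in Appendix A has its own heading and its own alternative. The adopted hypotheses and numbers are tabulated there, and the worked 288-lesion example shows how to turn them into RN counts. All of this stands. The Summary Statements are not the appendix's only formal design statement, and the appendix does contain what is needed to derive the correct counts.

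A reader might go further and infer that the protocol commits the trial to stopping after 13 lesions or ending at 65, or that it is badly underpowered because the 13/65 rule has power of only 0.54, and a 0.25 chance of stopping early, at RN 7.5%. The documents do not support this. Those figures arise only if a rule written for RN 5% is applied against the 7.5% target, and nothing directs that. They are not properties of this trial.

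The reply does not answer the mismatch in 4.4.3. If 4.4.3 is taken as the worded rule for the adopted row, it words that row incorrectly.

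**Conclusion.** The point holds in two parts. The 13/65 Summary Statement is an unlabelled leftover from an option not adopted. It is a clarity defect that leaves the 134 lesions and 49 patients unchanged. The substantive part is that 4.4.3 does not implement the row it relies on. With 14 RN in 134 lesions the adopted design rejects the supplement, while 4.4.3 claims success. That takes two-stage alpha from 0.047 to 0.077, or to 0.081 if 8 RN in 52 also continues, against a target of 0.05. The printed beta of 0.200 for the adopted row also does not reproduce: exact power at RN 7.5% is 0.856.

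These figures treat lesions as independent, as the plan does, and take R1 and R as rejection numbers, as the appendix defines them.

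**What to change.** 1. In Appendix A, mark the 124/288 and 13/65 designs as considered but not adopted, and mark 52/134 as the design in force.
2. Replace the Summary Statement with one for the adopted row: RN-free proportion of at most 0.85 versus at least 0.925; 52 lesions in stage 1, ending the trial if 44 or fewer are RN-free (8 or more RN); 134 lesions in total, rejecting the supplement if 120 or fewer are RN-free (14 or more RN); PET 0.528, average N 90.69, alpha 0.047, and exact power 0.856 at RN 7.5% under independent lesions, in place of the 0.80 implied by beta 0.200.
3. Reconcile 4.4.3 to that statement as the single governing rule: continue only with 7 or fewer RN in the first 52 lesions, and claim success only with 13 or fewer RN in 134.

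The cost is one replaced paragraph and labels in Appendix A, plus corrected counts in 4.4.3. It needs no extra patients, lesions or data. The one real consequence is that a final count of exactly 14 RN would no longer be a success.
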